4.3 Procedure for Accounting for Missing, Unused and Spurious Data

Missing data, e.g., due to withdrawal, protocol deviation or patient loss to follow-up will be summarised and patterns analysed. The proportion of missing values per variable will be presented. Where appropriate, differentiation will be made between partially completed and fully missing outcome data. For specific questionnaires their established, validated methods for managing missing item-level data will be adopted e.g., QUALEFFO-41. The main analyses will be performed using available cases only. If needed, a sensitivity analysis of the primary outcome (TUG at 12 months post-randomisation) will explore the effect of missing data on the primary outcome results using multiple imputation techniques. These will explore the possibility of data being missing at random as well as potential departures from this assumption if appropriate.

	Intervention			Control			Total		
			Missing			Missing			Missing
	Expected	Received	from	Expected	Received	from	Expected	Received	from
	n	n %	Expected	n	n	Expected	n	n	Expected
			n %			n %			n %
Baseline									
demographic									
TUG									
Baseline									
4-months									
8-months									
12-months									
Back pain									

Table 4. Summary of missing data at each point

Baseline							
4-months							
8-months							
12-months							
6MW							
Baseline							
4-months							
8-months							
12-months							
FR							
Baseline							
4-months							
8-months							
12-months							
TLS							
Baseline							
4-months							
8-months							
12-months							
QUALEFFO-41							
Baseline							
4-months							
8-months							
12-months							
Grip							
(dominant hand)							
Baseline							
4-months							
8-months							
12-months							
FES-I							
Baseline							
4-months							
8-months							
12-months							
SEE							
Baseline							
4-months							
8-months							
12-months							
Kyphosis					 	 	 

Baseline					
4-months					
8-months					
12-months					
EARS					
4-months					
8-months					
12-months					
GRC					
4-months					
EQ-5D-5L					
Baseline					
4-months					
8-months					
12-months					
Falls log					
4-months					
8-months					
12-months					
Healthcare					
diary					
4-months					
8-months					
12-months					

5. Trial Population and Descriptive Analyses

5.1 Participant flow and representativeness of study sample

The flow of participants through the trial from screening (number screened, meeting eligibility, willing to participate), randomisation, receiving treatment, to follow-up and inclusion in primary analyses will be summarised using a CONSORT flowchart (Figure 1). Reasons [24] Numbers of participants recruited and included and excluded in final analyses for the primary outcome will be displayed.

5.2 Withdrawal from treatment and loss to follow-up

The number and proportion of participants who withdraw along with timings of withdrawal from the trial, as well as the number of lost to follow up or excluded from the primary analysis will be summarised along with reasons in Table 5. Then used to inform Figure 1. If differential losses are identified, the reasons for these will be explored further.

Table 5. Loss to	follow-up and	withdrawal
------------------	---------------	------------

Time	Intervention	Control	Total, n (%)
Prior to treatment			
Withdrawn, n			
Loss to follow up, n			
Total, n (%)			
Before follow-Up 1 (4-month)			
Withdrawn, n			
Loss to follow up, n			
Total, n (%)			
Between follow-Up 1- 2 (8-month)			
Withdrawn, n			
Loss to follow up, n			
Total, n (%)			
Between follow-Up 2-3 (12- month)			
Withdrawn, n			
Loss to follow up, n			
Total, n (%)			
Total, n (%)			

Table 6. Reasons withdrawn or loss to follow up

Reason	Intervention	Control	Total , n (%)
Consent withdrawn			
SAE/AE/Medical conditions ^a			
Uncontactable			

Total

a. See Table 16: Adverse events and Serious Adverse events

5.3 Description of Compliance with Intervention

Treatment fidelity will be reported. The total number of trial physiotherapy sessions attended, and the number of these that were delivered virtually will be summarised for each group. Compliance with the intervention is defined as participating in the assessment and prescription of at least 3 adherence support techniques as recorded on treatment logs. Treatment session numbers and as well as the adherence strategies prescribed for the intervention group. We will display graphically the types and frequency with which adherence strategies were selected (Figure 2). We will summarise participant visits to healthcare professionals outside of the OPTIN trial, and those related to back pain to monitor total dose of physiotherapy (private and NHS) and back-related intervention, see Table 8.

		Intervention		Contr	ol
	Physiotherapy Session	Virtual session	Behavioural Techniques	Physiotherapy Session	Virtual session
	n	n	n	n	n
Assessment*					
Follow-up 1					
Follow-up 2					
Follow-up 3					
Follow-up 4					
Follow-up 5					
Follow-up 6					
Total (median IQR)					
Compliant n (%)					
Assessment and ≥ 3 techniques					

Table 7: OPTIN sessions attended and compliance.

*Extended 90 min for OPTIN arm. Virtual session = physiotherapy via telephone or video-call.

Figure 2. Adherence strategies selected (example)

Information about health care received outside of the trial i.e., number of health care visits, reason for visit (back related/ un-related), health professional seen (GP/Nurse/Physiotherapist/OT/Other), hospital stays is not expected to be normally distributed. Total visit numbers, number of physiotherapists visits, (private and NHS) reason for visit (back related/ unrelated) will be summarised for each group.

	Total	Intervention	Control
	n (%) median (IQR)	n (%) median (IQR)	n (%) median (IQR)
Number of health			
professional			
appointments			

Number of back-related		
appointments		
Number of		
physiotherapist		
appointments		
Private physiotherapist		
appointments		
NHS physiotherapist		
appointments		

5.4 Unblinding

This is an assessor only blinded trial. If trial assessors become unblinded to treatment group, they will treat this as a protocol deviation. Data about protocol deviations will be summarised and reported as part of safety reporting: see section 7.

5.5 Baseline Comparability of Randomised Groups

Standard descriptive statistics will be used to describe the characteristics of the two groups at baseline that is numbers with proportions for binary or categorical variables and either means (with SDs) or medians (with IQRs) for continuous variables as appropriate. Baseline comparability of the groups will be summarised including demographic characteristics and performance on primary and secondary outcomes as well as on other important prognostic factors e.g., co-morbidities, number of fragility fractures. In addition, thoracic kyphosis at baseline will be plotted for each group to better understand the distribution of spinal curvatures in the study population i.e., hypokyphotic (lower curvature), normal (mid) ranges of thoracic kyphosis, to moderate or severe hyperkyphosis (higher curvature). There will be no tests of statistical significance nor confidence intervals for differences between randomised groups on any baseline variable.

	Intervention (n = XX)	Control (n = XX)	All participants (n = XX)
Sex ^a			
Male			
Female			

Table 9: Demographic and baseline characteristics of participants

Age ^b (years)		
Height ^b (cm)		
Weight ^b (kg)		
BMI ^b (kg/m ²)		
Comorbidities score (wFCI) ^b		
BMD (g/cm ³) ^b		
T-score lumbar spine ^b		
Time since osteoporosis diagnosis ^b		
Number of vertebral fractures ^b		
Location of vertebral fractures ^a		
Upper thoracic (T1-T5)		
Lower thoracic (T6-T12)		
Upper Lumbar (L1, L2)		
Lower Lumbar (L3-L5)		
Last confirmed VFF ^b (months)		
Number of non-vertebral fractures ^b		
Type of non-vertebral fractures ^a		
Shoulder		
Wrist		
Нір		
Other Fragility Fractures		
Self-report mobility (walking) ^a		
 Unlimited 500m-1km 100-500m <100m Housebound Unable 		

Self-	report mobility (stairs) ^a		
1.	Normal		
2.	One step at a time		
3.	Down with rail		
4.	Up and down with rail		
5.	Unable down		
6.	Unable		
Self-	report mobility (support) ^a		
1.	None		
2.	Stick outdoors		
3.	Stick always		
4.	2 sticks		
5.	2 crutches		
6.	Walking frame		

a: binary and categorical data: n (%), b: continuous data: mean (SD) or median (25-75% quartiles), in either case the number of participants providing data will also be reported

Table 10: Baseline primary and secondary outcome measures

	Intervention	Control	All participants
	(n = XX)	(n = XX)	(n = XX)
Presence of back pain ^a			
In past 2 weeks			
Тодау			
Back pain intensity (NPRS 0-10) ^b			
In past 2 weeks			
Тодау			
Fall in past year ^b			
Needed medical attention			
Participants falling ^a			
1.Frequently (\geq 1/ week)			
2.Occasionally (\leq 1/ month)			
3. Rarely (≤ 1/ year)			
TUG (s) ^ь			
QUALEFFO-41 Total (points) ^b			

QUALEFFO-41 subscales (points) ^b		
Pain		
Physical Function		
Social Function		
General Health		
Mental Health		
Thoracic kyphosis (degrees) ^b		
Grip dominant hand (kg) ^b		
6MW (m) ^ь		
6MW exertion CR10-RPE (0-10) ^b		
Legs		
Breathing		
FR (cm) ^b		
TLS (s) ^b		
FES-I ^b		
SEE ^b		

a: binary and categorical data: n (%), b: continuous data: mean (SD), range or median (25-75% quartiles), range in either case the number of participants providing data will also be reported

5.6 Reliability

To ensure consistency and reliability of data processing, validation checks will be conducted. This will include checking for duplicate records, checking for missing data, checking the validated values for implausible values and validating potential outliers, and checking that data has been imported into statistical packages correctly. This will involve records from each site. Calculations and processes performed by computer e.g., QUALEFFO-41 calculations will be checked by hand calculations. These checks will be performed for 25 participants randomly sampled from the dataset. Clarification will be sought by comparing electronic datasets with case report forms.

6. Analysis

6.1 Methods used for analysis of primary outcome.

We will plot and display TUG data at all time points: 0, 4, 8 and 12-months to consider patterns of change over time and any outliers. At 12-months post-randomisation the two treatment groups will be compared on the primary outcome of the TUG measure using a multivariate linear regression model adjusting for recruiting centre (stratification factor), age at baseline and baseline TUG score. An unadjusted t-test will also be undertaken. As the TUG is recorded at 4 months and 8 months after randomisation as well, an additional analysis utilising all time points using multi-level modelling and including a treatment by time interaction, if appropriate, will be undertaken. For each of these models, the assumption of approximate normality will be assessed by examining the residuals. If this assumption is not met the first approach will be to consider a transformation to achieve normality. If this is not possible, the two groups will be compared using non-parametric methods (e.g., Mann-Whitney U-test). This analysis will be unadjusted and will consider each time point separately.

TUG (seconds)*	Intervention Mean (SD)	Control Mean (SD)	Mean difference (95% Cl)	p-value
Unadjusted 12- months				
Adjusted for baseline, centre and age				
Supporting analyse	25			
Repeated measure	S			
4 months				
8 months				
12 months				
12 months (per protocol)				

Table 11: Analysis of primary endpoint, TUG test change at 12-months

* A negative change corresponds to a better result at 12-months

6.2 Methods used for analysis of secondary outcomes.

Secondary outcomes which can be considered approximately continuous (QUALEFFO-41, FES-1, NPRS, TLS, Grip strength, 6MW, FRT, thoracic kyphosis, SEE and EARS) will be plotted over time and compared at 12 months using a multivariate linear regression model adjusting for recruiting centre (stratification factor), age at baseline and baseline score of the relevant variable as appropriate e.g. for the QUALEFFO-41 this would be baseline QUALEFFO-41. An unadjusted t-test will also be completed. An additional analysis using data at 4-, 8- and 12-months post-randomisation will also be undertaken using a repeated measures linear regression model. The appropriateness of the assumption of approximate normality will also be considered and transformation to normality or non-parametric methods used as appropriate. See Table 12.

Thoracic kyphosis is unlikely to be normally distributed, as in populations with vertebral fracture more people are likely to have moderate and severe kyphosis. [2, 25]. In addition, previous work has suggested the potential for change in thoracic kyphosis at follow-up is greater for those with the highest baseline values of kyphosis. [25] Therefore we will plot and display thoracic kyphosis values and consider a transformation to normality before comparison using parametric tests. If normality is not possible, non-parametric methods will be used.

	Intervention	Control	Mean Difference		
	Mean (SD) n	Mean (SD) n	(95% CI)	p-value	
QUALEFFO-41 (tota	al points)				
Unadjusted 12- months					
Adjusted for baseline, centre and age					
Supporting Analys	es				
4 months					
8 months					
12 months					
QUALEFFO-41 (pain)					
Unadjusted 12- months					

Table 12: Comparison between groups secondary outcomes, self-report questionnaires

Adjusted for baseline, centre and age						
Supporting Analyses						
4 months						
8 months						
12 months						
QUALEFFO-41 (phy	/sical)					
Unadjusted 12- months						
Adjusted for baseline, centre and age						
Supporting Analys	es					
4 months						
8 months						
12 months						
QUALEFFO-41 (soc	ial)					
Unadjusted 12- months						
Adjusted for baseline, centre and age						
Supporting Analys	es					
4 months						
8 months						
12 months						
QUALEFFO-41 (general)						
Unadjusted 12- months						
Adjusted for baseline, centre and age						
Supporting Analyses						

4 months				
8 months				
12 months				
QUALEFFO-41 (me	ntal)			
Unadjusted 12- months				
Adjusted for baseline, centre and age				
Supporting Analys	es			
4 months				
8 months				
12 months				
FES-I				
Unadjusted 12- months				
Adjusted for baseline, centre and age				
Supporting Analys	es			
4 months				
8 months				
12 months				
NPRS today (0-10)				
Unadjusted 12- months				
Adjusted for baseline, centre and age				
Supporting Analyses				
4 months				
8 months				
12 months				
NPRS last 2 weeks (0-10)				

Unadjusted 12- months				
Adjusted for baseline, centre and age				
Supporting Analys	es			
4 months				
8 months				
12 months				
SEE				
Unadjusted 12- months				
Adjusted for baseline, centre and age				
Supporting Analyses				
	es			
4 months				
4 months 8 months				
4 months 8 months 12 months				
4 months 8 months 12 months EARS-B				
4 months 8 months 12 months EARS-B Unadjusted 12- months				
4 months 8 months 12 months EARS-B Unadjusted 12- months Adjusted for baseline, centre and age				
4 months 8 months 12 months EARS-B Unadjusted 12- months Adjusted for baseline, centre and age Supporting Analyse	es			
Supporting Analysis 4 months 8 months 12 months EARS-B Unadjusted 12-months Adjusted for baseline, centre and age Supporting Analysis 4 months	es es es			
Supporting Analysis 4 months 8 months 12 months EARS-B Unadjusted 12-months Adjusted for baseline, centre and age Supporting Analysis 4 months 8 months	es 			

Table 13: Comparison between secondary outcomes, physical measures

	Intervention	Control	Mean Difference	
	Mean (SD) n	Mean (SD) n	(95% CI)	p-value
TLS (s)				

Unadjusted 12- months				
Adjusted for baseline, centre and age				
Supporting Analyse	es			
4 months				
8 months				
12 months				
Grip strength dom	inant hand (kg)			
Unadjusted 12- months				
Adjusted for baseline, centre and age				
Supporting Analyse	es			
4 months				
8 months				
12 months				
6MW (m)				
Unadjusted 12- months				
Adjusted for baseline, centre and age				
Supporting Analys	es			
4 months				
8 months				
12 months				
Functional Reach Test (cm)				
Unadjusted 12- months				
Adjusted for baseline, centre and age				

Supporting Analyses				
4 months				
8 months				
12 months				
Thoracic Kyphosis	(Degrees)			
Unadjusted 12- months				
Adjusted for baseline, centre and age				
Supporting Analyses				
4 months				
8 months				
12 months				

Falls are both a secondary outcome and important safety data. The nature, severity and outcome of falls will be reported as part of trial safety adverse event monitoring: see section 7 below. In addition, numbers and additional data about falls collected at baseline and from fall diaries will be reported and analysed. The number and proportion of participants who have a fall during follow-up will be summarised by treatment group and compared between the groups using a logistic regression model. This model will be adjusted for recruiting centre, age at baseline and whether or not the participant reported a fall in the previous year at baseline. Odds ratios will be reported along with 95% CIs and associated p-values. Amongst those participants who report at least one fall, the number of falls reported during follow-up will be summarised by treatment group using medians and IQRs and compared using a Mann-Whitney U-test. This will be repeated for falls that require medical attention. These analyses will be presented as outlined in Table 13. If a sufficient number of falls are reported this analysis may be reported considering each portion of follow-up (i.e., up to 4 months, from 4 to 8 months and from 8 to 12 months) separately.

	Intervention	Control	OR (95% CI)	p-value
Number of participants reporting a fall ^a				
Number of falls reported ^b			NA	

Table 14: Comparison between groups falls data.

Number of falls needing medical attention ^b		NA	
Number of falls in participants that previous reported falling in previous year at baseline ^b			

^a Summaries will be n (%); ^b Summaries will be median (IQR)

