3.3 Sample size

The primary outcome is the TUG test, a test of balance, lower limb strength and walking ability with established reliability and validity. It records the time in seconds (s) a person takes to stand up from a chair, walk 3 metres at a self-selected speed, turn and walk back and sit down, faster performance indicates better function. [10, 15] The MCID for the TUG has not been established in people with VFFs, but a MCID of 1.4 s is reported for similar older populations with chronic musculoskeletal disorders.[22] The study requires 104 participants (52 per arm) to be 80% powered to detect a 1.4s difference in TUG score between groups at a 5% significance level (two sided) assuming that the SD is 2.5s. Similar trials have had loss to follow-up rates of 10% at 12 months. To account for this the sample size is 116 participants (58 per arm).

Sample size calculations were performed in Stata v15 (StataCorp. 2017. *Stata Statistical Software: Release 15*. College Station, TX: StataCorp LLC).

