3.8 Statistical Analysis Outline

It is anticipated that all statistical analysis will be undertaken using Stata (StataCorp LP, www.stata.com) or other well-validated statistical packages such as SPSS. A blinded analysis of the data (not separated by treatment group) will be undertaken prior to the final data lock to look into the distribution of variables, missing data distributions, and to finalise the per protocol population.

Standard descriptive statistics will be used. Means and standard deviations (SDs) or medians (with lower and upper quartiles) as appropriate will be used for continuous variables, and numbers and percentages will be used for binary and categorical variables. Summary statistics will be presented for all comparative outcomes, and effect estimates will be reported together with 95% confidence intervals with all tests carried out at a 5% two-sided significance level.

The final analysis of all primary and secondary endpoints will be conducted together when all recruited patients have completed all follow-up. The study sample will be described, and then principal comparisons will be performed on an intention-to-treat basis, with a per-protocol analysis repeated at 12 months for the primary outcome, the Timed up and Go (TUG) test.

At 12 months post-randomisation the two treatment groups will be compared on the TUG measure using a multivariate linear regression model adjusting for recruiting centre (stratification factor), age and baseline TUG score. An unadjusted t-test will also be undertaken. An additional analysis utilising all time points will be undertaken. The assumption of approximate normality will be assessed by examining the residuals. If this assumption is not met the first approach will be to consider a transformation to achieve normality. If this is not possible, the two groups will be compared using non-parametric methods (e.g., Mann-Whitney U-test).

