4.1 Statistical Significance and Multiple Testing

A two-sided 5% significance level will be used throughout with 95% CIs presented. Since there is a single primary outcome in this study there is no concern regarding multiple testing, and all secondary outcomes will be considered as supporting the primary result.

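### If residuals look non-normal, the primary TUG analysis can end in an unadjusted rank test with no named effect estimate in seconds, a switch that 52 per arm does not need

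*SAP*

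**What the plan says.** Sections 3.8 and 6.1 of the SAP name a linear regression of 12-month TUG, adjusted for recruiting centre, age and baseline TUG, and add an unadjusted t-test. Normality is judged by examining residuals; no criterion is given. Both sections then say: "If this assumption is not met the first approach will be to consider a transformation to achieve normality". If that is not possible, section 6.1 continues: "the two groups will be compared using non-parametric methods (e.g., Mann-Whitney U-test). This analysis will be unadjusted and will consider each time point separately". Section 3.8 gives the same sequence without the word unadjusted.

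Mann-Whitney is only an example, but the absence of adjustment is fixed for whatever non-parametric method is used.

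Section 3.8 promises effect estimates with 95% confidence intervals. Table 11 has columns for means, SDs and a mean difference. No shift or median-difference estimator is named for the rank branch, and no back-transformation for the middle step.

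Section 6.2 gives the continuous secondary outcomes a similar route. For kyphosis it says: "If normality is not possible, non-parametric methods will be used".

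**The concern.** The trial is sized on a difference in seconds, so its primary result should be a difference in seconds with a confidence interval. Under the plan the quantity reported may be a mean difference, a difference on an unnamed transformed scale, or a rank comparison, and the choice is made by judgement after outcome models have been fitted.

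The last branch also removes the baseline value of the outcome and the factor on which randomisation was stratified. TUG is a timed test bounded below, so skewed residuals are quite possible and the rule may well be triggered. At stake are the interpretability of the primary result and, if baseline TUG predicts 12-month TUG well, its precision.

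**Working it through.** **Inputs from SAP section 3.3.** "The study requires 104 participants (52 per arm) to be 80% powered to detect a 1.4s difference in TUG score between groups". The test is two-sided at 5% and the assumed SD is 2.5 s. Loss to follow-up is 10%, giving 116 randomised. No baseline-to-12-month correlation r and no distributional shape are given; both are assumptions below.

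**1. The plan's own figure.** Two-sample t-test, 1.4/2.5 = 0.56 SD, two-sided 5%, 80% power: 51.03 per arm, rounded up to 52, so 104. Then 104/0.9 = 115.6, rounded up to 116. Both figures reproduce. The calculation uses no covariates.

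**2. Normal data, 52 per arm, 1.4 s.** Adjusted power is Φ(1.4 / [2.5·√(1−r²)·√(2/52)] − 1.96). For Mann-Whitney, 52 is multiplied by its efficiency relative to the t-test: 3/π under normality, 0.864 as the lower bound for shift alternatives.

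| Analysis | Power |
|---|---|
| Unadjusted, normal approximation | 0.815 |
| Adjusted, r = 0.3 | 0.849 |
| Adjusted, r = 0.5 | 0.909 |
| Adjusted, r = 0.7 | 0.979 |
| Mann-Whitney, efficiency 3/π | 0.797 |
| Mann-Whitney, efficiency 0.864 | 0.756 |

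**3. Precision in seconds.** The 95% half-width for an unadjusted mean difference is 1.984 × 2.5 × √(2/52) = 0.97 s. With baseline adjustment it is multiplied by √(1−r²): 0.84 s at r = 0.5 and 0.69 s at r = 0.7.

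**4. Moderately skewed data.** Simulation with log-normal TUG (mean 10 s, SD 2.5 s), 52 per arm, effect 1.4 s. The adjusted model has baseline as its only covariate and HC3 standard errors; centre and age are not simulated.

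| r (assumed) | Adjusted model | Mann-Whitney |
|---|---|---|
| 0.3 | 0.83 | 0.83 |
| 0.5 | 0.89 | 0.82 |
| 0.7 | 0.97 | 0.83 |

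Repeat runs differ by 0.01 to 0.03.

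**5. Does the adjusted model need rescuing?** Its null rejection rate with HC3 errors was about 0.04 to 0.055, including a heavier-skew case (mean 12 s, SD 5 s). With ordinary standard errors and other skewed shapes it was 0.042 to 0.052. Non-normal residuals do little harm to its type I error at this size.

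**6. Stronger skew.** With a shifted log-normal (SD 2.5 s, effect 1.4 s), power was:

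| Shape | r | Linear adjusted | Mann-Whitney | Baseline-adjusted rank |
|---|---|---|---|---|
| 0.5 | 0.3 | 0.828 | 0.926 | 0.942 |
| 0.5 | 0.5 | 0.891 | 0.935 | 0.976 |
| 0.5 | 0.7 | 0.962 | 0.931 | 0.996 |
| 0.8 | 0.3 | 0.833 | 0.994 | 0.997 |
| 0.8 | 0.7 | 0.942 | 0.994 | 1.000 |

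The rank test can beat the linear model, clearly so under strong skew. In each of these cases the rank analysis that keeps baseline does at least as well as the one that drops it.

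**The case against.** **The branch is a last resort.** This stands. The rank test is reached only if a transformation fails. If TUG is log-normal, a log transformation repairs it: in simulation, using Shapiro-Wilk as a stand-in for inspection, log-scale residuals failed in only about 5 to 7% of runs. Under that shape the plan would usually stop at an adjusted log model, which is efficient. The remaining criticism of that step is that neither the transformation nor a back-transformed estimate is named.

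**Planned power is not lost.** This also stands. The sample size assumed no covariates, so the fallback gives up extra precision, not the 80% on which the trial was sized. A reader might infer a large, certain power loss. The documents do not support that: they give no r, the design effect is 1.4 s, and the direction can reverse under skew.

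**An estimate could be added.** Section 3.8 promises effect estimates, and an empty table shell can be altered. True, but none is specified for this branch, and the analyst would be choosing it after seeing data.

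**Distributions are reviewed blind before lock.** Section 3.8 does provide this, and a transformation could be settled then. But section 6.1 ties the decision to residuals of the fitted models, and the SAP does not say that check is blinded.

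**Two competing primary tests.** A reader might infer from Table 11, where the unadjusted row sits above the supporting analyses, that either test may count as the result and that type I error is inflated despite section 4.1's "Since there is a single primary outcome in this study there is no concern regarding multiple testing". The text does not support this: it names the adjusted regression first and adds the t-test as a further analysis. The row order is only untidy.

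**Kyphosis.** Section 6.2 looks at the distribution of values, whereas the model's assumption concerns residuals. This is a side point on a secondary outcome and adds nothing to the case on TUG.

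**Conclusion.** The point holds, as a should-fix. Whatever r is, the final branch abandons adjustment for baseline TUG, age and the stratification factor, and neither fallback step pre-specifies an effect in seconds to compare with 1.4 s. The protection it offers is hardly needed, since the adjusted model's type I error stays near 5% under the skew examined with 52 per arm.

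The size of the power cost is conditional. With log-normal TUG (mean 10 s, SD 2.5 s) and 1.4 s it runs from nothing at r = 0.3 to 0.97 v 0.83 at r = 0.7. The fallback remains valid under the null and near planned power: about 0.80 under normality and about 0.76 at the efficiency lower bound. These figures rest on assumed r and shape and on simulations with baseline as the only covariate.

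**What to change.** In sections 3.8 and 6.1, state that the centre-, age- and baseline-adjusted linear model on the seconds scale is the primary analysis whatever the residuals look like. Keep the residual check as a diagnostic. If residuals are non-normal, report HC3 or bootstrap confidence intervals for the same mean difference.

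As sensitivity analyses only, name a log-scale model with a back-transformed estimate, or a rank analysis adjusted for baseline and centre, preferably with a shift estimate in seconds. Delete the sentence that makes the non-parametric analysis unadjusted. Apply the same rule to the continuous secondary outcomes in section 6.2, including kyphosis. As a tidy-up, list the unadjusted t-test among the supporting analyses in Table 11.

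The cost is SAP wording, settled before treatment groups are compared; no new data are needed. The statistical price is some efficiency if TUG is strongly skewed or truly log-normal. For example, at r = 0.7 and a smaller effect of 1.0 s, the adjusted log model had power of about 0.86 against 0.80 for the seconds-scale model. The sensitivity analyses would show whether that matters.
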